7.1 Specification of Safety Parameters

All abnormal and incidental findings during the physical encounters from the ARC visits will be documented on a case report form and reviewed by ARC physician within 24 hours.

The dietary and other biomarkers to be collected in this study are: plasma tocopherols/carotenoids, serum folate, serum B12, plasma fatty acids, lipid panel, IL-6, C-Reactive Protein and APOE4. Given the high cost of the biomarker, the main laboratory analyses will not occur until yrs 4-5 of the grant that is about 1-3 years after the blood draw. Since these values may not be meaningful after such a long period has elapsed and that in some cases the clinical implication of some of these biomarkers may be unknown, we will not provide biomarker information to the participant.

7.2 Methods and Timing for Assessing, Recording, and Analyzing Safety Parameters

The MHD for healthy participants- the target of this study- is generally safe. Should participants develop health problems during the study that precludes staying on this diet (e.g. unintentional weight loss, eating disorders), the participants are advised to contact primary physician and decide the merits of continuing in the study and are free to discontinue participation. Participants are asked to report any such developments.

7.3 Adverse Events and Serious Adverse Events.

An adverse event (AE) is generally defined as any unfavorable and unintended diagnosis, symptom, sign (including an abnormal laboratory finding), syndrome or disease which either occurs during the study, having been absent at baseline, or if present at baseline, appears to worsen. Adverse events are recorded regardless of their relationship to the study intervention.

A serious adverse event (SAE) is generally defined as any untoward medical occurrence that results in death, is life threatening, requires inpatient hospitalization or prolongation of existing hospitalization, results in persistent or significant disability/incapacity, or is a congenital anomaly.

7.4 Reporting Procedures

All abnormal and incidental findings during the study visits will be reviewed by the study physician, [name]., Ph.D. The abnormal findings will be documented on a case report form by [name] within 24 hours. If necessary, an adverse report will be generated.

Reporting: All adverse events will be compiled and reported in summary form on an annual basis to the Einstein IRB local CCI/IRB and at the conclusion of the study. Serious adverse events whether related to the study or not will be reported to the CCI/IRB and [name]., Chief, Behavioral & Systems Neuroscience Branch, Division of Neuroscience & NIA official on DSMB & [name], MS, DSMB Chair & Safety Officer by phone, email or fax upon discovery; for serious adverse events related to the study a completed local IRB Adverse Event Report will be submitted within 5 business days upon discovery to the Einstein IRB; serious adverse events unrelated to the study will be reported on the annual adverse events log submitted with the progress report to the Einstein IRB. All deaths will be reported to the IRB and Drs. [name] and [name] upon discovery by phone, email or fax upon discovery; a completed local CCI/IRB Adverse Event Report will be submitted within 10 days of initial CCI/IRB notification. All deaths will be reported to the CCI/IRB upon discovery. Deaths will be reported to the Einstein IRB within 30 days since last intervention.

7.5 Follow-up for Adverse Events

Adverse Events will be followed up on case-by-case basis until resolved or considered stable by the study physician.

8 INTERVENTION DISCONTINUATION

If participants have unintentional weight loss defined as 10% weight change, if BMI ≥ 25 and 5% weight change if BMI < 25 in past six months to one year or develop health issues that preclude participation in the study, the participant may be asked to withdraw or he/she may voluntarily withdraw from the study. Participants may withdraw voluntarily from participation in the study at any time and for any reason. Alternatively if the withdrawal is temporary (due to surgery or other health or other matter), they can be followed for study outcomes if practical and can rejoin study when ready. Each situation will be decided on a case by case basis.

We have considered an attrition rate of 15% from visit #1 to visit #2 and 5% thereafter between visits. However we may consider replacement of participants if the numbers projected for

attrition are higher –time permitting. If there is not enough follow-up time, then replacement will not be possible.

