4. MHD diet at home and outside the home: photo of contents of home fridge/contents of cupboard (photo-optional activity)
5. Monthly calls start as tailored to participant using motivational interviewing approach

Behavioral Component of the Intervention. We will use a motivational interviewing approach to enhance motivation for adherence to the intervention. We propose to use validated Social Cognitive Theory (SCT) constructs to implement the intervention with emphasis on the social-physical environmental (e.g. modification of the home environment) and behavioral (individual level) changes. The following principles will be applied to issues related to dietary change: self-monitoring, stimulus control, problem solving, goal setting and individual feedback. **Self-monitoring** promotes behavior changes by promoting awareness of eating habits and creates self-efficacy. Participants will be offered a variety of tools from web-based systems or apps such as MyFitnessPal or ChooseMyPlate super tracker or paper-based food diaries to self-monitor in a manner tailored to individual needs.

Attendance and **monthly self-monitoring of three days' intake** will be tracked as process measures to determine participant adherence. Non-adherent participants (as demonstrated by missed sessions or unreachable by phone) will receive up to ten additional phone contacts at different times of day/ day of week. If no contact is established after ten contacts, the participant will be considered as limited contact or no follow-up status. However, each participant will be considered on a case-by-case basis and contact may be established at a later date as determined by participant and study staff.

Participants in the experimental intervention arm will be exposed to an intervention over an 18 month period (four in-person visits in small groups with the interventionist over a two month intensive phase & monthly telephone coaching starting in month 3 of the intervention till month 18). Assessment visits cover a 27month period (run-in, baseline, months 9 & 18 and 27) at the Aging Research Center (Van Etten Building) at the Albert Einstein College of Medicine (Einstein). Participants in the intervention arm are expected to follow the diet over the 27 month period they participate in the study.

Sample Size and Population

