Visit #1: When judged to be compliant based on satisfactory completion of cognitive function by smartphone/tablet and dietary intake via ASA24, participants will be invited to Visit #1. At this visit there will be cognitive testing, a short review on use of the smartphone, and completion of questionnaires before randomization. A fasting blood draw to assess serum biomarkers associated with diet will be scheduled close to the date of the baseline visit, at which time weight and height will also be assessed. Anthropometric measures include height and weight for the calculation of body mass index (BMI), waist-hip measures and blood pressure. Measurement of weight will be recorded in kilograms. Scales will be calibrated with fixed known standard weights and certified annually by the local Bureau of Weights and Measures. Height will be recorded in centimeters and measured with a stadiometer attached to the wall. BMI in kg/m² will be calculated from measured weight and height. After Visit #1, participants will undergo cognitive and behavioral measurements in burst fashion for a 7-day period every nine months over a 27-month study period in tandem with completing 7 diet recalls. Daily measures of health behaviors such as sleep quality, physical activity, fatigue, stress/emotions, and social activity will be included along with the cognitive function measures over the one-week period (see Appendix for questionnaires.) Smartphones or tablets used for the burst measurements will either be mailed or returned after each burst when participants return for the blood draws.

Visit #2 will occur 9 months after baseline visit. At this visit, we will conduct cognitive testing along with a short refresher on use of smartphones to precede the 7 day burst measure for cognition and diet that follows this visit as well as after visits #2-4. Participants will be scheduled for the follow-up blood draw for serum biomarkers and anthropometric measures. **Visit #3** will occur 9 months after Visit #2 and will consist of cognitive testing and a similar refresher on use of smart-phone/ ASA24. The last **Visit #4** will occur 27 months after baseline or 9 months after visit # 4 and will include cognitive measurements.

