5.3.3 Prohibited Interventions

Any intervention that may impact exposure (diet) and outcome (cognition) are prohibited and included in exclusion list. These include the following:

- Participating in any diet or weight loss programs such as: Weight Watchers', Atkins or extreme dieting programs
- Participating in programs to enhance cognition such as playing brain games
- Taking medications that impact cognition such as Aricept, Ritalin and other medications for ADHD.

If participants are prescribed the above medications after randomization or they develop a health outcome that would have made them ineligible to participate in the trial (e.g. diabetes), they will

continue to be followed and the decision to continue in the study will be assessed on a case-by-case basis by investigators with input from the Data Safety Monitoring Board.

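### Section 8 ties unintentional weight loss to leaving the study rather than to stopping the diet; a cheap rewording would keep a few month 18 and 27 outcomes

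*Protocol*

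**What the plan says.** Protocol section 8 sets a weight-loss trigger of 10% (5% if BMI is below 25) over six months to a year, alongside health issues that rule out taking part. For either, "the participant may be asked to withdraw or he/she may voluntarily withdraw from the study". The one mention of outcome follow-up concerns short absences: "if the withdrawal is temporary (due to surgery or other health or other matter), they can be followed for study outcomes if practical". Each situation is left to individual judgement, and the section applies to both arms.

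Section 7.2 covers "health problems during the study that precludes staying on this diet (e.g. unintentional weight loss, eating disorders" and similar events. It sends the participant to a primary physician to "decide the merits of continuing in the study and are free to discontinue participation". The problem is with the diet, but the decision is about the study.

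Section 5.3.3 treats a comparable case differently. Participants who start a prohibited medication or develop a condition that would have excluded them will "continue to be followed and the decision to continue in the study will be assessed on a case-by-case basis", with input from the Data Safety Monitoring Board.

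Stopping the diet and leaving the study remain separate events after coaching ends at month 18: "Participants in the intervention arm are expected to follow the diet over the 27 month period they participate in the study" (Precis).

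**The concern.** A safety rule for a diet needs to be able to stop the diet. It does not need to end outcome collection. The bursts are completed at home on a study smartphone, and section 5.4 relies on this to keep people who move away. Weight loss does not in itself prevent anyone from completing a burst, so outcomes lost under this rule are mostly avoidable.

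The exposed data are Bursts 3 and 4. They enter the SAP's secondary longitudinal models, where the arm-by-time term summarises the treatment effect on change over time. If people who stop the diet also leave, those models lean towards those who stayed on it. The listed covariates and imputation variables contain no weight-change or discontinuation variable; the optional sensitivity analyses could add one.

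Burst 2, the primary time point, is little exposed. The first scheduled weight after baseline is at Visit 2 (section 6.1). Burst 2 follows that visit, with phones mailed back or "returned after each burst when participants return for the blood draws" (section 3). A self-reported loss could act earlier, because the trigger window starts at six months. However, section 3 already reports 260 of 290 at Visit 2, and missing Burst 2 scores are imputed.

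**Working it through.** **The plan's own figures**

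- Planned difference (section 9.2), effect size 0.35 SD and within-person correlation r = 0.9: 0.35 × √(2 × (1 − 0.9)) = 0.157, which the protocol rounds to 0.16.
- Attrition. Section 8 states: "We have considered an attrition rate of 15% from visit #1 to visit #2 and 5% thereafter between visits". 326 × 0.85 × 0.95 × 0.95 = 250, the planned number at Visit 4, so 5% applies per visit.
- Power with 125 per arm, two-sided 5% assumed: 79.0%, against 80% stated.

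**Inputs for the check**

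- 260 at Visit 2 (section 3), taken as 130 per arm.
- 5% loss per later visit: 260 × 0.95 = 247; 247 × 0.95 = 235. Per arm, 130 − 117.3 = 12.7 lost after Visit 2.
- *Assumed:* a fraction f = 2% to 10% of the MHD arm (2.6 to 13 people) leaves under section 8 after Burst 2. The 10% end is a ceiling, because 13 people is all of the planned later loss in that arm.
- *Assumed:* leavers have the full benefit at Burst 2 and none at months 18 and 27. Stayers have 0.157 at every burst. The documents give no task-level effect, so the composite's planned difference stands in for one task on a standardised scale.

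**Hand check, equal weights**

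With leavers kept, the true arm difference is 0.157 at month 9 and 0.157(1 − f) at months 18 and 27. With their later bursts lost, it appears as 0.157 throughout. The excess is 0, 0.157f and 0.157f at months 9, 18 and 27.

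- Slope excess = 9 × 0.157f / (81 + 0 + 81) = 0.157f/18 per month. At f = 0.10 this is 0.0105 per year.
- Fitted month-27 excess = 0.157f × (2/3 + 1/2) = 0.157f × 7/6. At f = 0.10 this is 0.0183.

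**Generalised least squares on burst means given baseline**

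This uses compound symmetry: conditional variance 1 − r² = 0.19 and covariance r − r² = 0.09 at r = 0.9. It simplifies the SAP's session-level models.

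| f | Arm-by-time excess per year (SE 0.0383) | Ratio to SE | Month-27 excess (SE 0.0535) | Ratio to SE |
|---|---|---|---|---|
| 0.02 | 0.0021 | 0.06 | 0.0037 | 0.07 |
| 0.05 | 0.0053 | 0.14 | 0.0092 | 0.17 |
| 0.10 | 0.0106 | 0.28 | 0.0184 | 0.34 |

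**Sensitivity, f from 0.02 to 0.10**

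- Half the benefit already gone at Burst 2: 0.0016-0.0081 per year; 0.0028-0.0140 at month 27.
- r = 0.85 (planned difference 0.19): 0.0026-0.0130 per year; 0.0045-0.0225 at month 27.
- r = 0.5 (planned difference 0.35): 0.0047-0.0237 per year; 0.0082-0.0411 at month 27. The largest month-27 ratio is 0.0411/0.1055 = 0.39 SE.
- Precision: at f = 0.10 the standard error of the arm-by-time term rises by 2%.

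**Cross-check by power**

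With 235 at month 27, power for 0.35 SD is 76.5%. Keeping 2, 5 or 10 people who would otherwise leave adds about 0.4, 0.9 or 1.8 points.

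**The case against.** The strongest reply is that the rule requires no loss of data. It is permissive, is decided case by case, and nothing in it forbids collecting Bursts 3 and 4 from someone who stops the diet. The trigger is narrow: a substantial unintentional loss on a diet meant to be eucaloric, where the protocol expects only small losses in some people. The effect falls on secondary models in a self-described pilot. All of this stands, and it is why the point is minor. What it does not remove is that section 8 never offers the option of stopping the diet while staying in follow-up.

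Four stronger readings are tempting, and the documents do not support them.

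- *Section 8 contradicts section 5.3.3.* Both end in individual discretion about continuing in the study. They differ in the default: 5.3.3 starts from continued follow-up and section 8 does not.
- *Dropout will differ by arm.* Section 7.2 names weight loss as a reason for not staying on the diet, which makes a link plausible. No rate by arm is given, and section 8 covers both arms.
- *The health-issue trigger should also stop the diet only.* It is defined as health issues that preclude participation in the study, so by its own terms it cannot be limited to the diet.
- *The SAP would discard bursts collected after someone stops the diet.* It would not. It defines a valid burst by session count, gaps and, for Burst 2, the visit window, so such bursts already enter the analyses.

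The Manual of Procedures and the text just before section 8 were not available, so practice may already be better than the wording.

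**Conclusion.** The point holds as a minor, inexpensive improvement. Section 8 gives withdrawal from the study as the only stated consequence of unintentional weight loss, and section 7.2 makes a similar link. This could lose a few Burst 3 and 4 outcomes that need not be lost.

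The size is not documented. The figures rest on an assumed 2-10% leaving rate in the MHD arm, complete loss of benefit among leavers, and the planned composite difference applied to a single task. Even at the 10% ceiling, the arm-by-time term is overstated by about 0.28 SE and the month-27 difference by about 0.34 SE (0.39 SE if r were as low as 0.5). A reader might infer that the primary result is at risk. The documents do not support that: the primary comparison is at Burst 2, is little exposed, and is analysed by intent to treat with multiple imputation.

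**What to change.** 1. Reword sections 8 and 7.2 so that the weight-loss criterion stops the diet and coaching only. The clinical thresholds stay as they are.
2. Ask those participants to complete the remaining smartphone bursts and assessments unless they are unable or withdraw consent for data collection.
3. Record the date and reason for each discontinuation and report them by arm.

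The SAP's rules for including bursts need no change.

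The cost is a wording change, simple tracking and participant payments. The retention plan in section 3 pays $20 per visit and $80 per burst, so $100 per time point, or up to $115 with the $5 and $10 bonuses. Under the assumed 2-10%, 2.6-13 people × 2 bursts = 5.2-26 time points. That comes to $520-$2,600 at $100, or $598-$2,990 at $115, and double if the comparison arm had the same rate.

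If all bursts have already been collected, only the report of section 8 withdrawals by arm, date and reason remains, and it is still worth doing.

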9 STATISTICAL CONSIDERATIONS

9.1 General Design Issues

The primary hypothesis is that participants randomized to the MHD diet will have more stable and possibly improved cognitive function relative to baseline, whereas comparison participants will have measurable decline.

The secondary hypothesis is that at baseline there will be no differences between arms in serum biomarkers indicative of a MHD diet pattern, specifically total folate, tocopherols, carotenoids, vitamin B12 and fatty acid profile; and self-reported intake of food groups such as fruits and green leafy vegetables; however at post-intervention, biomarkers of the MHD and self-reported intake will be higher in the intervention arm.

9.2 Sample Size and Randomization

Our initial design was to randomize 326 participants, with an expected 15% attrition at 9-months (Visit 2), and 5% per year thereafter to yield a total of 250 participants at 27 months after baseline (Visit 4). This would yield sufficient power for both the primary endpoint at 9 months, and final time point at 27 months. With 125 participants per arm at Visit 4, we would have 80% power to detect an effect size of 0.35 SD, representing an absolute between-group difference of 0.16 in the within-person change in cognition score. Assuming a within-person correlation of 0.85 (0.5), we would have had 80% power to detect an absolute difference of 0.19 (0.35) in the change in scores. In a previous study (ESCAPE), the correlation of mean performance (averaged across all assessments) from one burst to the next was ~0.90 (Personal Communication: [name], 7-6-2022). The 9-month timepoint was chosen as primary, as it was the time that potentially would have the greatest difference by arm due to the largest adherence.

Given the challenges with recruitment, due to the somewhat high participant burden of the protocol and challenges of the Covid-19 pandemic, we revised the sample size to an expected n=277 to be randomized. For our primary endpoint at 9 months, assuming 10% attrition (n=250), we will still have 80% power based on our original assumptions. Using pessimistic assumptions of 20% attrition at each 9-month visit, the power should be 54% based on n=143 at last follow up at 27 months or Burst 4 to detect these effect sizes.

Key secondary outcomes include between-arm comparisons of MHD related dietary intakes. Based on preliminary data from the Study of Latinos: Nutrition & Physical Activity Assessment Study, baseline mean (SD) for biomarker folate, alpha-tocopherol, and B12 are approximately 46 (17) nmol/L, 0.91 (0.28) mg/dL and 598 (330) pg/mL respectively (93). An effect size of 0.35 would be detectable with 80% power with 125 subjects per arm, a between-arm difference in change of at least 5.95 nmol/L, 0.10 mg/dL, and 116 pg/mL in these respective markers at 9 months assuming a within person correlation of at least 0.5.

Randomization

Stratified permuted block randomization with variable block sizes will be used to randomize participants to one of the two study arms in a 1:1 ratio. Randomization will be stratified on sex, age (<53, 53-65), and education level (no more than high school or equivalent, more than high school).

9.2.1 Treatment Assignment Procedures

The study statistician will generate the randomization lists, one for each strata, which will be uploaded into the study database. A randomization module will be created so that study staff remain blinded to study arm until after a participant has passed screening, signed the informed consent and is ready to be randomized.

9.3 Interim analysis and Stopping Rules

The study will be stopped for reasons of poor study performance such as slow accrual, high losses to follow-up or poor quality control.

While the possibility of this event is very low, should there be need to suspend the study due to safety issues such as high number of SAEs overall, the number of occurrences of a particular type of SAE, severe AEs/reactions, or increased frequency of events. Such findings are presented to the study statistician or to the Data and Safety Monitoring Board (DSMB) statistician to review the events by group to determine whether there are statistical as well as clinical concerns. The statistician reports his findings to a closed session of the DSMB or to the Safety Officer and/or NIA. The findings are used to determine what steps will be taken.

9.4 Outcomes

Primary Outcome:

The primary outcome is a global composite cognition score derived as an average of the three z-scores of the participant's performance on three of the M2C2 ambulatory cognitive assessments (Grid Memory, Symbol Search, and Color Shapes tasks) at 9 months post baseline. These assessments are validated measures of visuospatial memory, processing speed and short-term associative memory binding, respectively.

Secondary Outcomes

Several secondary outcomes relate to whether the MHD can be adapted for a diverse middle-aged cohort in the Bronx. We will evaluate the change from baseline for serum biomarkers indicative of a MHD diet pattern at 9 months, specifically total folate, tocopherols, carotenoids, vitamin B12 and fatty acid profile; and self-reported intake of food groups such as fruits and green leafy vegetables. In addition, secondary outcomes consist of performance on the individual ambulatory cognitive assessments (Grid Memory task, Symbol Search task, Color Shapes task)

contributing to the primary outcome to determine whether observed intervention effects are attributable to specific cognitive domains.

Exploratory Outcomes

The exploratory outcomes relate to short- and long-term associations between dietary patterns self-reported stress and affect collected during the M2C2 surveys, and all five of the ambulatory cognitive tasks, including two exploratory tasks related to long-term associative memory and working memory capacity (Shopping List and Rotation Span tasks). Short-term (momentary, day-to-day) and long-term (across 27 months of follow-up) associations between the intervention and the ambulatory assessments will be examined.

Because the laboratory specimens are analyzed in yr 4-5, the assessments relating to the diet biomarkers on the entire sample will not be available until later in the study. In addition there will be no interim analyses of outcomes because this is a low risk study of a pilot clinical trial of short duration and important end-points such as sustainability and timing of effects may not be observed if the trial is stopped early, we will not perform interim analyses. However we will monitor for safety and quality of conduct. We are assessing Alzheimer's Disease (AD) biomarkers P-tau 217 and neurofilament light chain (nfl) and other AD biomarkers. The clinical significance of these biomarkers in this younger age group is not known as little data exists for this age group. We are assessing these biomarkers to characterize these biomarkers in this population and age range. As these biomarkers were added after informed consent was obtained, we will send consent addendum documents by FedEx (or other expedited mailing system) or email or regular mail and ask that the signed consent be sent back by FedEx (or other expedited mailing system) or email, mail or text if needed. The consent is accompanied by a letter to the participants that describes why we are administering this new consent. The study coordinator will call the participants to introduce the consent as practically possible. Participants are free to call the study coordinator and principal investigator for questions they may have.

